## 6.6 Blood chemistries and blood count,

Blood chemistries including electrolytes (potassium, sodium, chloride and bicarbonate as well as calcium and blood urea nitrogen (BUN), and creatinine) will be measured at baseline and during the follow-up as part of the safety monitoring for hyperkalemia and renal insufficiency, as shown in Table 2. A complete blood count will also be collected at baseline and 6, and 12 months. Blood will be drawn after application of a tourniquet, by use of a small gauge needle, from an ante-cubital vein, and by an appropriately trained professional from subjects. These are part of assessing safety of the study drug and will be performed at the local Emory Clinical Laboratory.

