**7.2.3 Enrollment, Baseline, and Randomization:** During this phase, blood pressure measurements, detailed neuropsychological assessments, physical exam, brain MRI, and carotid ultrasound will be completed. Blood samples will also be collected for APOE, inflammatory and endothelial markers. Randomization and study intervention will occur after baseline data collection. Participants will then be started on the study medications. For all study related testing, the test results will not be disclosed to you unless deemed necessary by the study Physician.

**7.2.4 Follow-up Visits:** Following randomization, participants will be seen every two weeks, where antihypertensive study medications will be increased until they achieve blood pressure control (<140/90 mmHg), according to the designated trial protocol for blood pressure control. Blood pressure, heart rate, weight, adverse events (AE) and serious adverse events (SAE), pill count (to assess compliance), and use of non-study medications data will be collected. Once hypertension control is achieved, participants will be seen at 3, 6 and 12 months visits. Repeat neuropsychological assessment, blood draws (EPC and inflammatory markers), and urine collection will be conducted at the 6 and 12 months visit. Repeat neuroimaging and vascular ultrasound will be repeated at 12 months. BMP will also be checked at 2 weeks after randomization if only step one is needed, 4 weeks post randomization if treatment beyond step 1 is needed, and at 3, 6 and 12 months as shown in **Table 2**. Participants will also be contacted by phone as described in Table 2, Monthly during the follow-up phase. During these phone calls, participants will be asked about missing any doses in their medications and screened for any potential adverse events.

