clinical practice. Possible side effects include: dizziness, cough (lisinopril), weakness, fatigue, lower extremity edema and constipation (amlodipine), and hypotension. Renal failure and hyperkalemia are also potential complications of candesartan and lisinopril. HCTZ may cause renal failure, volume depletion, and hypokalemia. Lisinopril may cause a dry cough and angioedema. Beta blockers may be associated with weakness and bradycardia. Adverse events will be queried at each visit. Alternatives to antihypertensive medications include no therapy, which is not safe or ethical in patients with hypertension. Drug-drug interaction will be assessed by the study physician. If there is contraindication to use the candesartan or lisinopril and one of the other participant's medications then he/she will not be able to enroll in the study. If the contraindication is between an add-on agent (amlodipine, metoprolol, or HCTZ) then the participant will be enrolled but we will avoid using that agent as an add-on as described in section 5.3. Use of lithium is a contraindication for both lisinopril and candesartan and hence lithium users are excluded. The following combinations of medications are contraindicated for the add-on drugs: Simvastatin >20 mg with amlodipine, reserpine with metoprolol, and clonidine with metoprolol.

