## 8.2 Specification of Safety Parameters

The study medications may lead to adverse drug reactions (rash, edema, and in severe cases anaphylaxis) and uncomfortable side effects. If this occurs, the study medication will be discontinued and the subject's primary care provider notified. If the subject cannot tolerate the study medication, the study medication will be stopped and he/she will be referred to their primary care physician for ongoing hypertension treatment. The participant will however be continued in the study and asked to undergo the final visit evaluations. Subjects will be monitored carefully for symptoms, blood pressure control, and blood chemistry abnormalities during treatment, as described in the methods section above. A physician (PI) and trained personnel will be available at all times to respond to subjects' concerns. In the event of an emergency, resuscitation equipment is readily available in all the research areas where subjects are evaluated. Antihypertensive medications will also be adjusted up/down to maintain blood pressure below 140/90 mm Hg and above 100/45 mm Hg or at the discretion of the study physician for maintaining safety. For example, if blood pressure readings are high at their study visits but normal/low at home or the subject reports orthostatic dizziness the clinician will use his judgment to change the dosage of the study meds.

The subject's primary care physician will be informed of study plans. Frequent monitoring will include visits, blood pressure checks, laboratory testing and phone contact. Blood testing for kidney function and electrolytes (potassium) will be performed at baseline, 1, 3, 6 and 12 months. If needed, additional calls, visits, or laboratory testing will be conducted as decided by the PI and /or the primary care physician. If symptoms develop during any of the evaluations, procedures will be terminated immediately. The experimental procedures will be conducted in a well-supervised facility and subjects will be under constant observation by skilled professionals. Those who could not continue on the study medications will be asked to return for collection of outcome measure if they agree to return for the final assessment visit.

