#### **8.4 Methods and Timing for Assessing, Recording, and Analyzing Safety Parameters**

At each encounter, standardized adverse event (AE) monitoring forms will be completed. At any point during the study period an adverse event is identified, it will be recorded in the participant research record along with the time/place of the event. The study physician will be immediately notified and the participant evaluated either by phone (if participant is not on site) or face-to-face (if participant is on site). Depending on the physician assessment, further evaluation maybe performed such as scheduling additional visits, further lab work, exam, or referral to the emergency department. Details about the safety parameters will be recorded and entered into a database. Comparisons between the 2 groups will be conducted to assess overall and between group differential safety.

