#### 10.4 Outcomes

Table 3 provides a list of main outcomes. Other Analyses' variables: Logical memory, digit span, DSST, WMH volume, regional brain measures

**Table 3:** Independent, primary and secondary outcomes and other variables to be used in the analyses

Independent:	Randomization Group (Candesartan vs Lisinopril)
Primary outcome:	Executive function (EXAMINER score)
Secondary Imaging outcomes:	Perfusion, CO2 VR, VMR, FA, MD, DTT t-scores, rs-fMRI
Mediators:	CIMT, stiffness, inflammatory markers, EPC
Tertiary outcomes:	memory, digit span, DSST, WMH volume, regional brain measures
Stratification variable:	Race, number of antihypertensive medications
Covariates:	Prior stroke and prior use of ACEI/ARB
Safety:	AE, SAE, incident dementia

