#### 10.5 Data Analysis

The 2 groups will be compared on baseline demographics, education level, physical function (SPPB), IADL, DEX, mood (CESD), cognitive and vascular/inflammatory measures and APO-E genotype. Also, baseline WMH, perfusion, VR, lacunar infarcts, and hippocampal volumes will be compared between the 2 groups using independent t-tests, nonparametric rank-based tests, or chi-square tests as appropriate. We will compare number of AE, SAE and incident dementia in the 2 groups as part of our safety analysis using Fisher's exact test; adverse event categories will utilize MedDRA (Medical Dictionary for Regulatory Activities) coding. To assess possible bias due to selective dropout, baseline comparisons between participants who complete vs. do not complete 12-month outcome assessments will be performed. To assess if equivalent blood pressure was achieved in both groups we will compare mean SBP and DBP in both groups during the follow-up visits. In addition, % controlled (defined as SBP<140 mm Hg/90 mm Hg) will be calculated for each visit post-titration. We will compare the % control in both groups using chi-square.

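### Potassium and creatinine are collected for safety, but the specified safety analysis is limited to event counts, so a between-arm difference below the stopping limits could be missed

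*Combined protocol and SAP*

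**What the plan says.** Section 8.1 names the harms: "Renal failure and hyperkalemia are also potential complications of candesartan and lisinopril". Section 6.6 gives the purpose of the chemistry panel: "as part of the safety monitoring for hyperkalemia and renal insufficiency".

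Table 2 places the panel at screening, once in titration, and at 3, 6 and 12 months. Section 7.2.4 times the titration draw: "BMP will also be checked at 2 weeks after randomization if only step one is needed", otherwise at week 4. Section 8.2 gives a different schedule: "Blood testing for kidney function and electrolytes (potassium) will be performed at baseline, 1, 3, 6 and 12 months".

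On analysis, the safety row of Table 3 (Section 10.4) reads "AE, SAE, incident dementia". Section 10.5 says "We will compare number of AE, SAE and incident dementia in the 2 groups as part of our safety analysis", by Fisher's exact test, with MedDRA coding of adverse event categories. Section 8.4 adds a general statement: "Comparisons between the 2 groups will be conducted to assess overall and between group differential safety".

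Section 8.8 gives increased potassium and increased creatinine as examples of adverse events that need follow-up, without a cut-off. The only numerical limits are for exclusion (Section 4.2: potassium 5.5, creatinine 1.99 mg/dl) and for discontinuation (Section 9: potassium 5.8, creatinine 2.5 mg/dl). Section 8.9 specifies that the DSMB report tabulates AEs and SAEs by group, and lets the DSMB ask for more data and analyses.

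**The concern.** The trial compares two drugs that share these two harms, and it collects about four post-randomization values per participant to watch for them. The places where analyses are specified, Table 3 and Section 10.5, do not use those values. A rise that stays below the discontinuation limits enters the comparison only if it is recorded as an AE, and no rule says when it should be.

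Section 10.5 already treats blood pressure in the fuller way: it compares mean SBP and DBP at follow-up visits and also the percentage controlled. The safety chemistry gets neither.

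What is at stake is the between-arm evidence. A report of no difference in adverse events could stand beside laboratory values that do differ, and a laboratory analysis chosen after unblinding would be post hoc.

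**Working it through.** The plan states no figure for laboratory safety, so there is none to reproduce.

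**Inputs from the documents.** 70 per arm (Sample Size and Population); two-sided alpha 0.05 (Section 10.5); Fisher's exact test (Section 10.5); four post-randomization draws, one in titration plus months 3, 6 and 12 (Table 2); potassium limits 5.5 (Section 4.2) and 5.8 (Section 9), read as mEq/L.

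**Assumptions, not in the documents.** Potassium mean 4.2-4.4, SD 0.4-0.5, normal values, within-person correlation 0.5 between draws, true shift 0.2 mEq/L. Cut-offs 5.2 and 5.0 are used only to see how the answer moves. They are not proposed as limits.

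**Step 1: what Fisher's test needs, free of any SD assumption.** With 70 per arm, 5 events against 0 gives p = 0.058 and 6 against 0 gives p = 0.028. Six events against none is the minimum.

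**Step 2: share of participants ever above a cut-off c.** With z = (c − mean)/SD and correlation ρ, the share is 1 − ∫ φ(u) [Φ((z − √ρ·u)/√(1 − ρ))]⁴ du. At mean 4.4 and SD 0.45, a shift of 0.2 gives 2.5% vs about 7.1% above 5.5, and about 0.4% vs 1.4% above 5.8.

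**Step 3: Fisher power.** Exact enumeration of both binomials with 70 per arm, shift 0.2:

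| Values counted as events | Mean 4.4, SD 0.45 | Range over mean 4.2-4.4, SD 0.4-0.5 |
|---|---|---|
| above 5.8 | about 0% | at most 1% |
| above 5.5 | 11% | about 0-18% |
| above 5.2 or 5.0 | 44% or 58% | about 13-64% |

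**Step 4: comparing mean values at one visit.** The normal approximation is power = Φ[(shift/SD)·√(n/2) − 1.96], with √(70/2) = 5.92.
- SD 0.5: 0.4 × 5.92 − 1.96 = 0.41, so 66% (65% by the t distribution).
- SD 0.4: 0.5 × 5.92 − 1.96 = 1.00, so 84%.
- Adjusting for the pre-treatment value at r = 0.5 divides the SD by 1/√(1 − 0.25), that is, multiplies it by 0.866. Power becomes about 77% (SD 0.5) and 92% (SD 0.4).

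Means did better than counts in every case tried.

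**Step 5: larger shift.** For 0.3 mEq/L at mean 4.4 and SD 0.45, Fisher power is 1% above 5.8, 40% above 5.5, 83% above 5.2 and 92% above 5.0. A comparison of means has 98%, and above 99% when adjusted.

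**Step 6: creatinine.** The documents give no SD, so only SD units are possible. The difference detectable with 80% power is (1.96 + 0.84) × √(2/70) = 0.47 SD, or 0.47 × 0.866 = 0.41 SD adjusted at r = 0.5. No event-count calculation for creatinine is offered.

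**The case against.** The strongest reply is that laboratory safety is not absent. Section 8.8 treats raised potassium or creatinine as possible AEs, so such values can reach the Fisher test. Section 8.2 lists chemistry abnormalities among what is monitored, and Section 8.4, on analysing safety parameters, promises group comparisons. The DSMB may also ask for more.

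This stands in part. A reader might infer that the plan ignores laboratory data, or that a real difference would be reported as no difference. The documents do not support either reading: some raised values can be counted, and a difference could be missed, not must be. But Section 8.4 names no variable, time point or method, Section 8.8 gives no cut-off, MedDRA coding sorts only events already recorded, and a DSMB request is contingent.

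The second reply is that near-zero power depends on counting only values above 5.8 or 5.5, a rule that the plan does not contain. That is correct. With lower recording cut-offs the gap narrows considerably, so one near-zero figure should not be quoted alone.

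Third, a mean shift of 0.2 mEq/L is not itself the named harm, and the stated aims are cognition, imaging and mechanisms. This bears on weight. Individual participants remain covered by the monitoring in Section 8.2, the follow-up in Section 8.8 and the discontinuation criteria in Section 9.

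**Conclusion.** The concern holds as an under-specified analysis of moderate weight. The general promise in Section 8.4 is not carried into Section 10.5 or Table 3, where only counts of AE, SAE and incident dementia are analysed.

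Under the stated potassium assumptions and a 0.2 mEq/L shift, the count-based test has anywhere from about 0% to 64% power, depending mainly on which values come to be recorded as AEs. A comparison of the values themselves has 65-84%, or about 77-92% with baseline adjustment. The direction holds across the range tried; the size of the gap depends on a recording rule that the plan leaves open. For creatinine the argument is one of principle, since no SD is available.

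**What to change.** Add to the safety analysis in Section 10.5 and to the safety row of Table 3:

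1. The between-arm difference with 95% CI in potassium and in log creatinine at the post-randomization visits, from a mixed model adjusted for the pre-treatment (screening) value.
2. The number of participants per arm whose highest post-randomization value exceeds each limit already in the protocol, counted from the laboratory file whether or not an AE was recorded. Put the same table in the DSMB report (Section 8.9).

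Two points must be settled in the text for the model to be well defined:
- **Baseline value.** Section 7.2.1 places the pre-treatment panel at the screening visit, before the taper, and Table 2 shows no panel at the baseline visit, while Section 8.2 lists a baseline test. State which value is used and reconcile the sections.
- **Early draw.** Section 8.2 says month 1; Table 2 and Section 7.2.4 say week 2 or week 4. These must be reconciled.

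The cost is one model and one table from data already collected. The drawback is that the screening value is taken on prior antihypertensive drugs; this affects both arms alike. No clinical limit or management rule changes.

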## 3. STUDY DESIGN

This is a double-blind randomized clinical trial in individuals with hypertension and executive MCI without dementia. Participants will be treated for 1-year with candesartan or lisinopril. Additional antihypertensives will be added to achieve blood pressure control to below 140/90 mm Hg in both groups. Our study will recruit 160 participants to achieve a sample size of 140 with 70 participants in each group. Our outcome measures include cognitive function, cerebral perfusion and reserve, markers of vascular brain damage, atherosclerosis, stiffness, vascular inflammation and endothelial function.

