### **5.3 Concomitant Interventions**

The goal of the trial intervention is to achieve a blood pressure <140/90 mm Hg in at least 90% of the participants. To achieve blood pressure control, we will use a stepwise protocol as follows: candesartan 8 mg→16 mg→32 mg or lisinopril 10 mg→20 mg→40 mg. Both groups will also receive, if needed to achieve blood pressure control, HCTZ 12.5 mg→25 mg, Amlodipine 2.5 mg →5 mg→10 mg and metoprolol 12.5 mg→25 mg (extended release)→50 mg (extended release). Antihypertensive medications will be increased every 2 weeks until blood pressure control (less than 140/90 mm Hg) is achieved. Based on our prior study, we anticipate being able to achieve blood pressure control within 4-8 weeks in the majority of the participants. Only the candesartan and lisinopril treatments are blinded. The remaining treatments (HCTZ, Amlodipine, and Metoprolol) are open-label. In the instance where a participant cannot receive an add-on agent, e.g. if there is a history of allergy or intolerance to one of the add-on drugs (HCTZ, Amlodipine, and Metoprolol) or a contraindication due to drug-drug interaction (e.g. simvastatin dose >20 mg and amlodipine), then that add-on agent will be skipped and the next add-on drug will be used.

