### **10.2 Randomization**

The study un-blinded biostatistician will provide oversight of randomization fidelity and blinding. To ensure equal distribution between the 2 groups on important confounders, we will use block randomization with stratification on:

- (1) race, (white, non-white).
- (2) number of antihypertensive medications (2 or less vs >2).

Randomization will occur in a 1:1 allocation. Four separate randomization lists will be prepared (race=white, medications=2 or less; race=white, medications>2; race-non-white, medications=2 or less; race=non-white, medications>2). Randomization will use a computerized random number generator (SAS, V9.3); the blocking number will not be revealed to investigators or research staff. Each randomization list will include the treatment group allocation, a unique allocation sequence number, and a blank field (to complete with subject study ID as randomization occurs). Randomization lists will be provided to the IDS Pharmacy. Only the pharmacy and the un-blinded statistician will have access to the randomization lists. As the pharmacist is notified that an individual subject is eligible for randomization to a given stratum, the pharmacist will select the appropriate randomization list, complete the subject ID, and prepare the appropriate blinded study product. The pharmacist will enter the subject ID, date of product randomization, and the unique allocation sequence number on a web-based data form. The statistician will monitor appropriateness of randomization (eligibility criteria met, correct stratum used, next allocation sequence used) in real time; incorrect randomizations will be immediately recorded as protocol deviations and reported to the principal investigator (in a blinded fashion).

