#### Outcome Analysis

(a) Candesartan and cognitive/neuroimaging outcomes: General linear models will be used to compare the candesartan and lisinopril groups. Our main explanatory variable is the indicator for treatment group. Dependent variables will be the 12-month cognitive and neuroimaging measurements. For the cognitive analyses, our primary outcome is the executive function score derived using item response theory as outlined above in the EXAMINER methodology to account for education, age, and race influences on measures of executive abilities (developed by our collaborator, [name] team). For the cognitive outcome Mixed models with repeated measures (3 measurements) will be used. This procedure allows us to model the covariance structure to account for the potential variability across subjects in times of follow-up visits. Our main explanatory variable is the indicator for treatment group. The test of treatment effects on trial outcomes will be an interaction of treatment by visit (baseline,12 months follow-up). The main covariate adjustments will include history of prior stroke and prior exposure to ACEI/ARB. Additional covariate adjustments will be selected based on baseline statistically significant differences between the 2 randomized groups. The neuroimaging outcomes include measures of global perfusion, reactivity, FA, MD, and tractography metrics described above. **Table 3** provides a list of main variables. The multivariate models of the neuroimaging analysis will include the baseline values of the 12-month outcome variable, randomization stratification variables and other covariates that are significantly differ (at p<0.05) between the 2 groups at baseline. We will assess if the effects of randomized treatment are independent of blood pressure by comparing models with and without blood pressure change from baseline to 12 months. Summary statistics will include the model-adjusted mean and 95% confidence interval for each treatment group, and the mean (95% confidence interval) group difference on each 12-month outcome, as well as a p-value for group differences. All tests of significance on treatment group comparisons will use a two-sided alpha of 0.05.

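### The plan asks whether achieved blood pressure was equivalent, but sets no margin and no interval, so a non-significant difference cannot answer the question

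*Combined protocol and SAP*

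**What the plan says.** Section 10.5 (Data Analysis) states both the purpose and the method for mean pressure: "To assess if equivalent blood pressure was achieved in both groups we will compare mean SBP and DBP", at the follow-up visits. It then defines percent controlled against the 140/90 threshold at each visit after titration and adds: "We will compare the % control in both groups using chi-square".

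No test is named for the means. The only general rule is under Outcome Analysis in the same section: "All tests of significance on treatment group comparisons will use a two-sided alpha of 0.05". That part also promises 95% confidence intervals for the group difference, but on the 12-month outcomes, and Table 3 (section 10.4) does not list blood pressure as an outcome. No equivalence margin, two one-sided tests procedure or interval-within-margin rule appears anywhere in the document.

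Two other parts bear on the point. Section 5.3 sets a control target: "The goal of the trial intervention is to achieve a blood pressure <140/90 mm Hg in at least 90% of the participants". Outcome Analysis also plans to compare treatment-effect models with and without blood pressure change from baseline to 12 months.

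**The concern.** The aim is to show that two things are alike, while the one named tool tests whether they differ. Failing to find a difference is not evidence that it is small. Without a margin, there is no statement of how small would be small enough. Without an interval, the reader cannot see which differences the data leave open.

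At stake is interpretation. The rationale (sections 2.1 and 2.2) credits any advantage of candesartan to AT2-related effects rather than to pressure lowering. Comparable achieved pressure supports that reading, and the design does not guarantee it. Drugs are titrated to a threshold (section 5.3), and section 8.2 tolerates values well below it, so two arms could have the same percent controlled and different mean pressures.

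**Working it through.** **The plan's own figure.** There is none to reproduce. The document gives no margin, power or on-treatment SD for blood pressure, and the calculation in section 10.6 concerns cognitive and imaging outcomes.

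**Inputs from the document**
- 70 completers per arm. Section 3: "Our study will recruit 160 participants to achieve a sample size of 140 with 70 participants in each group".
- Allocation. Section 10.2: "Randomization will occur in a 1:1 allocation".
- Two-sided alpha 0.05 (Outcome Analysis).
- Reference control rate 90% (section 5.3).
- Three follow-up visits, at 3, 6 and 12 months (Table 2).

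**Assumptions**
- Systolic SD 15 mm Hg, range 12 to 18.
- Correlation between visits 0.3 to 0.7.
- Gaps and margins of 5 and 10 mm Hg. These are illustrative; the document supports no particular value.

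**Step 1: systolic mean, one visit.** SE = SD × √(2/70). The 95% half-width is 1.96 × SE. Power for a true 5 mm Hg gap is Φ(5/SE − 1.96), the other tail being negligible.

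| SD | SE | 95% half-width | Power for a 5 mm Hg gap | Chance the gap is non-significant |
|---|---|---|---|---|
| 12 | 2.03 | 4.0 | 69% | 31% |
| 15 | 2.54 | 5.0 | 50% | 50% |
| 18 | 3.04 | 6.0 | 38% | 62% |

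**Step 2: three visits averaged, SD 15.** The SE is multiplied by √[(1 + 2ρ)/3].
- ρ = 0.3: factor 0.730, SE 1.85, half-width 3.6, power for 5 mm Hg 77%.
- ρ = 0.7: factor 0.894, SE 2.27, half-width 4.4, power for 5 mm Hg 60%.

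**Step 3: percent controlled, 90% versus 80%.** The pooled rate is 0.85.
- Null SE = √(2 × 0.85 × 0.15/70) = 0.0604.
- SE under the alternative = √(0.9 × 0.1/70 + 0.8 × 0.2/70) = 0.0598.
- Power = Φ[(0.10 − 1.96 × 0.0604)/0.0598] = Φ(−0.31) = 38%. The gap is missed 62% of the time.
- Example: 63/70 versus 56/70 gives an uncorrected chi-square p of 0.098. The 95% CI for the difference is 10 ± 1.96 × 5.98 points, or about −1.7 to 21.7 points.
- At 90% in both arms the half-width is 1.96 × √(0.18/70), or 9.9 points.

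**Step 4: what an equivalence rule would deliver.** Two one-sided 5% tests are the same as requiring the 90% CI to lie inside the margin M. With no true difference, power = 2Φ(M/SE − 1.645) − 1, or zero if that is negative. At SD 15 and one visit:
- M = 5: 2Φ(1.972 − 1.645) − 1 = 26%.
- M = 10: 2Φ(3.944 − 1.645) − 1 = 98%.

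With the three visits averaged, M = 5 gives 71% (ρ = 0.3) to 42% (ρ = 0.7).

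Requiring a 95% CI inside the margin would be stricter. At SD 15, one visit and M = 5, it gives 2Φ(1.972 − 1.960) − 1, or about 1%, even when the arms are identical.

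**The case against.** The best defence is that the plan does not rest the attribution question on this check. It compares models with and without blood pressure change, both arms are treated to the same target with the same add-on drugs, and blood pressure is not an outcome in Table 3. The check stands beside baseline and dropout comparisons, and no primary or secondary estimate depends on it.

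Much of that stands. The adjusted models do bear on whether an effect is independent of pressure, and they soften the consequence. They do not settle it: they use only the change to 12 months, they condition on a variable measured after randomisation, and they do not ask whether pressures were alike during follow-up. A shared target makes a large gap less likely but does not measure it.

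Four stronger readings are tempting, and the documents do not support them:
- *Blood pressure would confound the trial.* Achieved pressure arises after randomisation. A gap would be a possible pathway of the treatment effect, and the intention-to-treat comparison would remain valid.
- *The sample is the cause.* A difference test cannot show equivalence at any size. With a wide enough margin, 70 per arm can suffice (98% at 10 mm Hg, SD 15).
- *A non-significant p-value will be reported as equivalence.* The plan states no decision rule. The risk is that it offers nothing else on which to base such a statement.
- *The plan specifies a difference test for the means.* That is inferred from the comparison of means and the two-sided alpha. Only chi-square is explicit.

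The single-visit figures are also the pessimistic end, since the plan refers to follow-up visits in the plural.

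**Conclusion.** The point holds as a mismatch between aim and method. As written, section 10.5 cannot support a statement that blood pressure was equivalent, because it has no margin and no interval.

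The size of what could go unnoticed depends on assumed values, since the document gives no on-treatment SD and no between-visit correlation. Over the assumed range, a non-significant result at one visit leaves open systolic differences of several mm Hg. Averaging three visits reduces the uncertainty but does not remove it. The percent-controlled test is weak by itself: its 38% power depends only on 70 per arm and the 90% versus 80% scenario.

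The consequence is confined to the claim that a cognitive or imaging effect is independent of pressure. This should be corrected, but it does not threaten the primary comparison.

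**What to change.** In section 10.5:

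1. Estimate the between-arm SBP and DBP differences over all post-titration visits with one repeated-measures model, and report each with a confidence interval.
2. Report percent controlled as a risk difference with a confidence interval, instead of relying on the chi-square p-value.
3. Then choose one of two options. Either drop the word equivalent and describe the differences and their intervals, or keep it and claim equivalence only if the 90% CI lies inside a margin that the investigators fix and justify before unblinding. Margins are needed for SBP, DBP and percent controlled. If an interval crosses its margin, say that equivalence was not shown.
4. Keep the models with and without blood pressure change as a supporting analysis, and say that they do not test equivalence.

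The cost is SAP wording; all the data are already collected. The downside of keeping the word equivalent is that the trial may have to report that equivalence was not shown, which is likely with a tight margin (26% power at 5 mm Hg, SD 15, one visit) and unlikely with a wide one (98% power at 10 mm Hg). Using all the visits helps. Dropping the word avoids that risk and still gives readers what they need.
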